4.4.1 Nausea and Vomiting

Prophylactic antiemetic therapy may be used in this study at the discretion of treating physician. Because of the potential of benzodiazepines to interact with DSF, the use of benzodiazepines for antiemetic prophylaxis should be reserved for patients who cannot be satisfactorily managed otherwise.

4.4.2 Diarrhea

Antidiarrheal medications will not be used prophylactically; however, patients will be instructed to take loperamide, 4 mg, at the occurrence of the first loose stool and then 2 mg every 2 hours until they are diarrhea-free for at least 12 hours. During the night, patients may take 4 mg of loperamide every 4 hours. Fluid intake should be maintained to avoid dehydration.

4.4.3 Central Nervous System Effects

Doses of 500-1000 mg of DSF per day with adjuvant temozolomide produced neurological toxicities in some patients, including delirium/psychosis, ataxia, and peripheral neuropathy, especially at the 1000 mg dose. Patients should be carefully monitored for early signs of these symptoms. Once other causes such as tumor progression are ruled out, dose reduction of DSF to 125 mg (half of 250 mg tablet) once a day should be considered if the toxicity is grade 2 or greater (refer to Section 6.2). If symptoms are not improving with dose reduction, DSF should be discontinued. Patients whose symptoms are not considered immediately life-threatening should be carefully monitored. Each patient may be approached individually with a systematic assessment to rule out other causes. Appropriate tests may include vital signs measurement, computerized tomography, MRI scans, or other appropriate medical assessment.

If the patient's level of consciousness is considered to be life-threatening, the patient should be hospitalized and necessary measures should be instituted to secure the airway, ventilation, and intravenous access.

4.4.4 Management of Disulfiram-Alcohol Reaction

In severe reactions caused by the patient's excessive ingestion of alcohol, supportive measures to restore blood pressure and treat shock should be instituted. Potassium levels should be monitored, particularly in patients on digitalis, since hypokalemia has been reported.

4.5 Duration of Therapy

Patients demonstrating continued benefit from the adjuvant temozolomide after 6 cycles can continue treatment to a maximum of 12 cycles.

If at any time the constraints of this protocol are considered to be detrimental to the patient's health and/or the patient no longer wishes to continue protocol therapy, the protocol therapy should be discontinued and the reason(s) for discontinuation will be documented.

In the absence of treatment delays due to adverse events, DSF-Cu treatment may continue until:

- Documented and confirmed disease progression
- Death
- Adverse event(s) that, in the judgment of the investigator, may cause severe or permanent harm or which rule out continuation of study drug
- Patient develops unacceptable toxicity deemed possibly, probably, or definitely related to drug that does not resolved to grade 1 or to the patient's baseline status
- Patient requires more than 1 dose reductions
- General or specific changes in the patient's condition render the patient unacceptable for further treatment in the judgment of the investigator
- Serious noncompliance with the study protocol
- Lost to follow-up
- Patient withdraws consent
- Investigator removes the patient from study
- The investigator, or the investigator's institution decides to close the study

In the case of tumor progression, both temozolomide and DSF-Cu should be discontinued, and patient should be considered for second-line therapy. If temozolomide is temporarily withheld due to toxicity, DSF-Cu should be continued until temozolomide may be resumed again. If temozolomide is discontinued, DSF-Cu may be continued as per the discretion of the treating physician. If DSF-Cu is discontinued due to toxicity, temozolomide may be continued as per the discretion of the treating physician.

4.6 Duration of Follow-up

Patients are evaluated for adverse events for 30 days after the last dose of DSF-Cu or until death, whichever occurs first. Patients removed from study for unacceptable adverse events will be followed until resolution or stabilization of the adverse event. Follow-up after the conclusion of the study participation will be per routine clinical care. Two years after the patient goes off study, the patient’s chart will be reviewed to collect data on progression and survival.

5.0 RESPONSE ASSESSMENT

For the purposes of this study, patients should be evaluated for response approximately every 8 weeks.

Response and progression will be evaluated in this study using the updated RANO response assessment criteria for high-grade gliomas (Wen, et al. 2010).

Criteria for Determining First Progression Depending on Time from Initial Chemoradiotherapy

First Progression	Definition
Progressive disease < 12 weeks after completion of chemoradiotherapy	Progression can only be defined using diagnostic imaging if there is new enhancement outside of the radiation field (beyond the high-dose region or 80% isodose line) or if there is unequivocal evidence of viable tumor on histopathologic sampling (eg, solid tumor areas [ie, > 70% tumor cell nuclei in areas], high or progressive increase in MIB-1 proliferation index compared with prior biopsy, or evidence for histologic progression or increased anaplasia in tumor). Note: Given the difficulty of differentiating true progression from pseudoprogression, clinical decline alone, in the absence of radiographic or histologic confirmation of progression, will not be sufficient for definition of progressive disease in the first 12 weeks after completion of concurrent chemoradiotherapy.
Progressive disease ≥ 12 weeks after chemoradiotherapy completion	
 1. New contrast-enhancing lesion outside of radiation field on decreasing, stable, or increasing doses of corticosteroids. 2. Increase by ≥ 25% in the sum of the products of perpendicular diameters between the first post-radiotherapy scan, or a subsequent scan with smaller tumor size, and the scan at 12 weeks or later on stable or increasing doses of corticosteroids. 3. Clinical deterioration not attributable to concurrent medication or comorbid conditions is sufficient to declare progression on current treatment but not for entry onto a clinical trial for recurrence. 4. For patients receiving antiangiogenic therapy, significant increase in T2/FLAIR non-enhancing lesion may also be considered progressive disease. The increased T2/FLAIR must have occurred with the patient on stable or increasing doses of corticosteroids compared with baseline scan or best response after initiation of therapy and not be a result of comorbid events (eg, effects of radiation therapy,

First Progression	Definition
	demyelination, ischemic injury, infection, seizures, postoperative changes, or other treatment effects).

Criteria for Response Assessment Incorporating MRI and Clinical Factors (Adapted from (Wen, et al. 2010).

Response	Criteria
Complete response	
 • Requires all of the following: complete disappearance of all enhancing measurable and non-measurable disease sustained for at least 4 weeks. • No new lesions; stable or improved non-enhancing (T2/FLAIR) lesions. • Patients must be off corticosteroids (or on physiologic replacement doses only) and stable or improved clinically. Note: Patients with non-measurable disease only cannot have a complete response; the best response possible is stable disease.
Partial response	
Requires all of the following:
 
 • $\geq 50\%$ decrease compared with baseline in the sum of products of perpendicular diameters of all measurable enhancing lesions sustained for at least 4 weeks. • No progression of non-measurable disease. • Stable or improved non-enhancing (T2/FLAIR) lesions on same or lower dose of corticosteroids compared with baseline scan; the corticosteroid dose at the time of the scan evaluation should be no greater than the dose at time of baseline scan. • Stable or improved clinically. Note: Patients with non-measurable disease only cannot have a partial response; the best response possible is stable disease.
Stable disease	
Requires all of the following:
 
 • Does not qualify for complete response, partial response, or progression. • Stable non-enhancing (T2/FLAIR) lesions on same or lower dose of corticosteroids compared with baseline scan. In the event that the corticosteroid dose was increased for new symptoms and signs without confirmation of disease progression on neuroimaging, and subsequent follow-up imaging shows that this increase in corticosteroids was required because of disease progression, the last scan considered to show stable disease will be the scan obtained when the corticosteroid dose was equivalent to the baseline dose.
Progression	
Defined by any of the following:
 
 • $\geq 25\%$ increase in sum of the products of perpendicular diameters of enhancing lesions compared with the smallest tumor measurement obtained either at baseline (if no decrease) or best response, on stable or increasing doses of corticosteroids*. The absolute increase in any dimension must be at least 5mm when calculating the products. • Significant increase in T2/FLAIR non-enhancing lesion on stable or increasing doses of corticosteroids compared with baseline scan or best response after initiation of therapy* not caused by comorbid events (e.g. radiation therapy, demyelination, ischemic injury, infection, seizures, postoperative changes, or other treatment effects). • Any new measurable lesion.

Response	Criteria
	
 • Clear clinical deterioration not attributable to other causes apart from the tumor (e.g. seizures, medication adverse effects, complications of therapy, cerebrovascular events, infection, and so on) or changes in corticosteroid dose. • Failure to return for evaluation as a result of death or deteriorating condition; or clear progression of non-measurable disease.

- NOTE. All measurable and non-measurable lesions must be assessed using the same techniques as at baseline.
- Abbreviations: MRI, magnetic resonance imaging; FLAIR, fluid-attenuated inversion recovery.
- Stable doses of corticosteroids include patients not on corticosteroids.

5.1 Evaluation of Best Overall Response

The best overall response is the best response recorded from the start of the treatment until disease progression/recurrence (taking as reference for progressive disease the smallest measurements recorded since the treatment started).

The patient's best response assignment will depend on the achievement of both measurement and confirmation criteria.

Summary of the RANO Response Criteria (Adapted from (Wen, et al. 2010).

Criterion	CR	PR	SD	PD
T1 gadolinium enhancing disease	None	≥ 50% ↓	< 50% ↓ but < 25% ↑	≥ 25% ↑*
T2/FLAIR	Stable or ↓	Stable or ↓	Stable or ↓	↑*
New lesion	None	None	None	Present*
Corticosteroids	None	Stable or ↓	Stable or ↓	NA†
Clinical status	Stable or ↑	Stable or ↑	Stable or ↑	↓*
Requirement for response	All	All	All	Any*

Abbreviations: RANO, Response Assessment in Neuro-Oncology; CR, complete response; PR, partial response; SD, stable disease; PD, progressive disease; FLAIR, fluid-attenuated inversion recovery; NA, not applicable.

* Progression occurs when this criterion is present.

† Increase in corticosteroids alone will not be taken into account in determining progression in the absence of persistent clinical deterioration.

NOTE: Patients may continue on treatment and remain under close observation and evaluation at 4-8 week intervals if there is uncertainty regarding whether pseudoprogression may be present as determined by the investigators. If subsequent radiographic or clinical assessments suggest that the patient is in fact experiencing progression, then the date of progression should be the time point at which this issue was first raised. Similarly, stable disease may be assigned in cases of presumed “pseudoprogression” associated with decreased steroid use.

5.2 Duration of Response

Duration of overall response: The duration of overall response is measured from the time measurement criteria are met for complete response (CR) or partial response (PR) (whichever is first recorded) until the first date that recurrent or progressive disease is objectively documented (taking as reference for progressive disease the smallest measurements recorded since the treatment started).

The duration of overall CR is measured from the time measurement criteria are first met for CR until the first date that progressive disease is objectively documented.

Duration of stable disease: Stable disease is measured from the start of the treatment until the criteria for progression are met, taking as reference the smallest measurements recorded since the treatment started, including the baseline measurements.

5.3 Neurological Exam and Performance Status

Patients will be graded using the ECOG scale and their neurological function evaluated as improved, stable or deteriorated in addition to objective measurement of tumor size. These parameters will be used to determine the overall response assessment.

5.4 Progression-Free Survival

PFS is defined as the duration of time from start of treatment to time of progression or death, whichever occurs first.

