2.0 STUDY OBJECTIVES

2.1 Primary Objective

1. To determine evidence of an antitumor effect in patients with unmethylated glioblastoma treated concurrently with DSF-Cu and concurrent radiation and temozolomide. To determine *6 month PFS and 12 month OS of patients with unmethylated glioblastoma treated with DSF-Cu in combination with concurrent radiation and temozolomide.*

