4.0 TREATMENT PLAN

This study is a single arm, open-label, phase II study of DSF-Cu in combination with concurrent temozolomide and radiation therapy followed by DSF – Cu and adjuvant temozolomide for patients with unmethylated tumors.

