4.3 Study Evaluations

Consistent with standard of care, patients will be seen approximately every 4 weeks. At each visit, a ECOG evaluation and corticosteroid usage (mg per day) will be recorded. Brain MRI will be obtained every 8 weeks to assess for radiological response. Quality of Life (QOL) will be assessed using the Edmonton Symptom Assessment System – Revised (ESAS-r) questionnaire. Subjects will be monitored for copper levels on Day 1 (+/- 7 days) of Cycle 1 and Cycle 4 of adjuvant temozolomide.

Patients are evaluated for adverse events for 30 days from the last treatment of DSF-Cu, or until death, whichever occurs first. Patients removed from study for unacceptable adverse events will be followed until resolution or stabilization of the adverse event. Patients will also be removed from the study for non-compliance.

Table 2: Potential Adverse Events Related to DSF

MedDRA Term	Frequency: Likely: greater than 10% Less Likely: 1-10% Rare: 1% or less
Neoplasms	Rare: Tumor necrosis
Blood and lymphatic system disorders	Rare: Neutropenia, anemia, leukopenia, thrombocytopenia, lymphopenia (likely due to temozolomide)
Immune system disorders	Rare: Hypersensitivity
Metabolism and nutrition disorders	Likely: Alcohol intolerance, metallic or garlic-like aftertaste
Psychiatric disorders	Less Likely: psychosis, delirium (need to rule out tumor progression)
Nervous system disorders	Likely: Drowsiness, headache, confusion Less Likely: ataxia, gait disturbance, peripheral neuropathy Rare: Extrapyrarnidal symptoms
Eye disorders	Rare: Optic neuritis
Cardiac disorders	Less Likely: Tachycardia, hypotension (need to rule out DSF-alcohol reaction)
Respiratory, thoracic, and mediastinal disorders	Less Likely: Dyspnea (need to rule out DSF-alcohol reaction)
Gastrointestinal disorders	Likely: Nausea, vomiting, diarrhea Less Likely: constipation (likely due to temozolomide)
Hepatobiliary disorders	Rare: Hepatitis
Skin and subcutaneous tissue disorders	Less Likely: Allergic dermatitis
Musculoskeletal	Rare: Arthralgia, myalgia
Renal and urinary disorders	Rare: Dysuria, hematuria
Reproductive system	Less likely: impotence
General disorders	Likely: Fatigue

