9.0 STUDY CALENDAR

Screening/baseline evaluations are to be conducted within 4 weeks (+/- 7 days) prior to start of protocol therapy. Scans will be performed prior to the start of the protocol therapy. Each treatment cycle is 28 days.

	Screening / Baseline	Weekly during radiation treatment	Start of Fourth Week of radiation therapy	Day 1 of Each Cycle (+/- 7 days)	End of Every Even-Numbered Cycle	Day 1 of Cycle 1 (+/- 7 days)	Day 1 of Cycle 4 (+/- 7 days)	End of Treatment	Follow-Up ¹
Informed consent	X								
H&P incl. neurologic exam, ECOG	X			X				X	
Evaluation of corticosteroid usage	X		X	X					
CBC	X	X		X					
CMP	X			X					
Copper, blood	X					X	X		
Pregnancy testing (if applicable)	X								
Edmonton Symptom Assessment System – Revised (ESAS-r) QOL Questionnaire	X		X	X				X	
Brain MRI prior to enrollment	X				X ²			X	
Temozolomide				Concurrent radiation with temozolomide on days 1-42 at 75 mg/m ² . ³ Responding patients will subsequently receive adjuvant TMZ 150 mg/m ² Days 1-5 of each following 28 day cycle ³					
Disulfiram				Days 1-28 of each cycle ⁴					
Copper gluconate				Days 1-28 of each cycle ⁴					
AE assessment			X	X	X	X	X	X	X

1. Follow-up will be as clinically indicated. A chart review will be done at 2 years after the last dose of DSF to look for progression and survival.
2. A confirmatory MRI should be considered in 8 weeks after documentation of complete response (CR) or partial response (PR) if consistent with the institutional standard of care
3. To be taken at bedtime on an empty stomach. Must not be taken within an hour of DSF.
4. To be taken two times a day with meals.
5. AEs will be tracked for 30 days after the last dose of DSF.

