10.0 STATISTICAL CONSIDERATIONS

10.1 Definition of Primary Endpoints and Analytical Plan

The co-primary endpoints will be ORR and PFS6. ORR will be defined as the percentage of patients with CR or PR according to the RANO criteria as described in Section 6.0. PFS6 will be defined as proportion of patients that are free from progressive disease (PD) as per RANO criteria or death at 6 months from the date of the first dose of DSF-Cu. PFS6 and median PFS will be estimated using the Kaplan-Meier product-limit method. For unmethylated glioblastoma receiving temozolomide without DSF-Cu, an ORR of less than 10% and PFS6 of less than 20% (Quinn, et al. 2009).

To justify future use of or drug development of DSF-Cu for glioblastoma, we hypothesized that the addition of DSF-Cu to temozolomide would improve ORR to 20% or increase PFS6 to 30%. The sample size is calculated based on the above hypotheses with one-sided exact test at an approximate α level of 0.10 and 80% statistical power. At these type I and II error rates, 14 -20 patients will detect a proportion of patients who have ORR significantly higher than 5% or PFS6 significantly higher than 10%. Of note, previous phase II study testing addition of O⁶-benzylguanine (a MGMT inhibitor) to temozolomide for temozolomide-resistant glioblastoma used similar hypothesis and observed a disappointing ORR of 3% and PFS6 of 9% (Quinn, et al. 2009). This negative phase II study has detailed information on ORR, PFS, and OS as well as associated estimated 95% CIs and will serve as a historical comparison for this study.

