10.2 Definition of Secondary Endpoints and Analytical Plans

The secondary endpoints will be toxicity, and OS.

1. Toxicities that are possibly/probably/definitively related to DSF will be graded by NCI CTCAE version 4.0 (2009) and will be tabulated by type and grade.
2. OS will be measured from the date of the first dose of DSF+Cu to the date of death or, otherwise, the last follow-up date on which the patient was reported alive. Median OS and OS12 (proportion of patients that are alive at 12 months) will be estimated using the Kaplan-Meier product-limit method.

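### PFS and the co-primary PFS6 start from different events, and the plan gives no start day for DSF-Cu, so time zero can differ by 0 to 9.5 weeks

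*Combined protocol and SAP*

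**What the plan says.** **Time origins.**
- Section 5.4: "PFS is defined as the duration of time from start of treatment to time of progression or death, whichever occurs first". The start of treatment is not tied to a named agent or day.
- Section 10.1: PFS6 is the proportion free of RANO progression or "death at 6 months from the date of the first dose of DSF-Cu". PFS6 is co-primary with ORR.
- Section 10.2: "OS will be measured from the date of the first dose of DSF+Cu to the date of death". This is the only definition of OS. OS12 is a secondary endpoint here, although Section 2.1 puts "6 month PFS and 12 month OS of patients with unmethylated glioblastoma" in the primary objective.

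**When DSF-Cu is given.**
- Section 4.0 describes "DSF-Cu in combination with concurrent temozolomide and radiation therapy", followed by DSF-Cu with adjuvant temozolomide. Sections 1.11 and 2.1 agree. The 42-day concurrent temozolomide diary (Appendix D) tells patients to keep temozolomide an hour apart from disulfiram and copper, so it assumes that they are already taking them.
- Section 4.2 gives the dose and frequency of DSF-Cu but no start day.
- The study calendar (9.0) gives the disulfiram and copper rows as "Days 1-28 of each cycle" and sets the cycle length at 28 days. The 42-day radiation phase appears only in the temozolomide row.
- Section 4.3 refers to "Cycle 1 and Cycle 4 of adjuvant temozolomide", and the Optune rule in Section 4.4 also places Day 1 of Cycle 1 after radiation.

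**The concern.** A landmark endpoint such as PFS6 needs one dated time zero. Two are given for progression-free survival, and they agree only if DSF-Cu begins on the first day of chemoradiation. The plan nowhere states that day, and the calendar, which sites use to schedule treatment, reads as if DSF-Cu belonged to the adjuvant cycles.

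Two things are at stake. First, the 6-month landmark moves with the origin. Second, if DSF-Cu starts later than other protocol therapy, a patient who progresses or dies in between never receives a first dose and so has no time zero under 10.1. No rule says how to count that patient. Section 4.2 resumes temozolomide after the rest only in patients with stable or responding disease, so under the calendar reading such patients could exist.

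**Working it through.** **Plan's own figures.** The plan gives no figure for a gap between origins. The relevant design figures in 10.1 are a PFS6 of 10% to be exceeded, a target of 30%, a one-sided exact test at about 0.10 and 80% power, with 14-20 patients. The smallest N meeting both error rates for PFS6 is 18: with 4 or more successes, alpha is 0.098 and power 0.835. This lies within the stated range and is used below.

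**Gap between origins.** The gap is the concurrent phase plus the rest.
- Treatment plan (4.0), DSF-Cu starting with radiation: 0 weeks.
- Literal calendar, durations from 4.2 (42 days plus two to three weeks): 6 + 2 = 8 to 6 + 3 = 9 weeks.
- With the upper radiation length in 1.11: 6.5 + 3 = 9.5 weeks.
- A patient who starts DSF-Cu late has a gap equal to the delay.

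With 6 months = 365.25/2/7 = 26.1 weeks, a gap of 8 to 9.5 weeks is 31-36% of the PFS6 window and 15-18% of a 12-month window. The 7-day allowance around Day 1 of a cycle could widen it slightly.

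**Illustration A: no events before Cycle 1, constant hazard after it (assumed).** If P is PFS6 from Cycle 1 and s the gap, the hazard is h = -ln(P)/26.1 per week. The rate at 6 months from the start of radiation is exp(-h × (26.1 - s)).

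| P from Cycle 1 | s = 8 | s = 9 | s = 9.5 |
|---|---|---|---|
| 10% | 20.3% | 22.1% | 23.1% |
| 30% | 43.4% | 45.4% | 46.5% |

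The change is 10.3 to 13.1 points at 10% and 13.4 to 16.5 points at 30%. Against 30 - 10 = 20 points, that is 51% to 83%. With N = 18 and 4 or more successes, the probability of passing is 0.098 at a true rate of 10%, 0.51 at 20.3% and 0.63 at 23.1%: same patients, different clock.

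**Illustration B: constant hazard from the start of radiation (assumed).** If 30% are event-free at 6 months from radiation:
- Counting everyone, 0.30^((26.1 + s)/26.1) = 20.7% (s = 8) to 19.4% (s = 9.5) are event-free 6 months after Cycle 1. Power at N = 18 falls from 0.835 to 0.53-0.47.
- Counting only patients event-free at Cycle 1, the rate is 30% again, but 31-35% of patients had an event before time zero (1 - 0.691 to 1 - 0.645).

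**Direction.** Let E be the proportion event-free at Cycle 1 and h the hazard after it. The rate from radiation is E × exp(-h × (26.1 - s)). The rate from Cycle 1 among those still event-free is exp(-h × 26.1). Their ratio is E × exp(h × s). With h set by 30% at 6 months from Cycle 1, the two are equal at E = 69.1% (s = 8) or 64.5% (s = 9.5). Above that, the later origin gives the lower PFS6; below it, the higher.

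**The case against.** The strongest reply is that concurrent dosing is stated, not just implied. Sections 1.11, 2.1 and 4.0 place DSF-Cu alongside radiation, and the diary handed to patients for the 42 radiation days presupposes it. The calendar wording can be read as daily dosing, in contrast to temozolomide on Days 1-5, and the column spans of that table cannot be confirmed from the extracted text. On this view the two origins name nearly the same day and only wording needs tidying.

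Much of this stands. A reader might infer from the calendar that DSF-Cu is withheld until the adjuvant phase and that every PFS6 will be dated 8 to 9.5 weeks late. The documents do not support that, because four places point to a concurrent start. The reply does not remove the conflict between 5.4 and 10.1, supply the missing start day, or cover a patient whose DSF-Cu starts after radiation has begun.

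The size is also open to challenge. Illustration A allows no event, not even a death, for 8 to 9.5 weeks. The RANO rules in Section 5.0 limit progression calls in the first 12 weeks after chemoradiation but do not exclude deaths. That objection is sound, so the figures are an illustration, not an estimate.

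**Conclusion.** The conflict in time origin is real and affects a co-primary endpoint. Its size is 0 weeks if DSF-Cu starts with chemoradiation, and 8 to 9 weeks (9.5 with the longer radiation course in 1.11) under a literal calendar reading. Under Illustration A, the later origin changes PFS6 by 10 to 16.5 points; other hazard assumptions shrink, remove or reverse that change.

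Four stronger readings are not supported:
- That the shift equals the difference the trial is sized to detect. It is about half to four-fifths of 20 points, and only under Illustration A.
- That OS12 has competing clocks. OS has one definition; OS12 moves only because the date of the first DSF-Cu dose is not fixed.
- That early failures will be dropped. No text says so. They simply have no time zero in 10.1 if DSF-Cu has not begun.
- That no benchmark comparison is possible. A mismatch of clocks arises only if DSF-Cu starts later than other protocol therapy.

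The point should be settled before analysis. It does not show that the trial's result is biased.

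**What to change.** Use one origin in Section 5.4, Section 10.1 (PFS6) and Section 10.2 (OS): the first day of any protocol therapy. State that every patient who starts protocol therapy is counted, including those who progress or die before a first DSF-Cu dose. The disulfiram and copper rows of the calendar must be reconciled with Sections 1.11, 2.1 and 4.0 and Appendix D on when DSF-Cu is given, and Section 4.2 should then state the start day. Which start is intended is for the sponsor to settle.

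The cost is wording in four sections and two calendar rows, with no extra data, because the first date of protocol therapy will be on record for each patient.
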